Ejaculatory Function	X					X	X
Adverse Events			X	X	X	X	X
Concomitant Meds	X	X	X	X	X	X	X

C Procedures

1 Visit 1: Screening

- Informed consent will be obtained prior to any research-related procedures.
- A physical including a digital rectal exam (DRE) will be performed.
- The subject's medical history and concomitant medications will be discussed and documented.
- The subject's vital signs will be taken and documented.
- The subject will complete the following questionnaires:
 - The AUA symptom score
 - BPH Impact Scale

- Bladder Function
- Erectile Function
- Ejaculatory Function
- The subject will undergo uroflow testing and will provide a post-void residual urine measurement.
- Blood (about 10 ccs or 2 teaspoons) will be drawn for CBC with platelets and PSA testing.
- A urinalysis (dipstick) will be performed.
- Dispense a Bactrim DS (antibiotic) 160/800mg tablet orally twice a day [Cipro (generic is permissible) 500 mg twice a day] with instructions to take for 1 day prior to biopsy, day of biopsy, and for 1 day following biopsy (total of 3 days).
- Subjects will be instructed to stop taking alpha blocker medications 7 days prior to biopsy.

2 Visit 2: Biopsy

- The subject's concomitant medications will be discussed and documented.
- The subject's vital signs will be taken and documented.
- A urinalysis (dipstick) will be performed to ensure that no infection is noted or suspected.
- Dispense an antibiotic
- Prostate size is measured via transrectal ultrasound on patients after receiving a Fleet's enema the morning of the examination.
- Transition zone biopsies will be performed.

3 Visit 3: Injection (4 weeks post-biopsy, ± 3 days)

- The subject's concomitant medications will be discussed and documented.
- The subject's vital signs will be taken and documented.
- Any adverse events experienced by the subject will be documented.
- **Injection Procedures:** onaBoNT-A solution does not contain a preservative, it should be administered within 4 hours after reconstitution and within 30 minutes of drawing into the syringe. The drug should be stored in a refrigerator when not in use during this period.
 - **Patient Preparation**
 - a. Patient is examined and submits urine for urinalysis which is examined by standard dipstick analysis or microscopic examination prior to randomization and preparing onaBoNT-A solution to ensure that no infection is noted or suspected.

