 - f. The needle is passed from posterior to anterior through the peripheral zone (PZ) on the right side into the base of the prostate at the transition zone/central zone junction on the left side. The needle is advanced to superior (bladder base) aspect of the transition zone.
 - g. The 1.0 ml of solution is first deposited at the inferior (apex) transition zone (TZ). The needle is withdrawn to the inferior (apex) transition zone/central zone junction and the second 1.0 ml of solution is deposited on the same side as the needle is withdrawn.
 - h. The needle, syringe, and vial are disposed of in a biohazard container according to institutional policy, and a witness signs a form.
 - i. After the injection, the patient remains in the clinic until a spontaneous void has occurred.
- Subjects will receive an adequate supply of tamsulosin/placebo with instructions on dosing.

- Because of the theoretical possibility of diffusion of onabotulinumtoxinA into seminal fluid, and no evidence to the contrary, those patients who engage in sexual intercourse are required to use condoms for 48 hours after the injection.

4 Visits 4 (Day 3 post-injection)

The subjects will be contacted by telephone 3 days after injection to monitor for symptoms of infection or bleeding.

5 Visits 5 (1 Week \pm 3 days post-injection)

The subjects will be contacted by telephone 1 week after injection to collect medical events, concomitant medication update, and status.

6 Visit 6: (4 Weeks post-injection \pm 3 days)

- The subject's concomitant medications will be discussed and documented.
- The subject's vital signs will be taken and documented.
- Any adverse events experienced by the subject will be documented.
- The subject will undergo uroflow testing and will provide a post-void residual urine measurement.
- A urinalysis (dipstick) will be performed.
- The subjects returned drug product packaging will be reviewed and discussed with him. A new supply of tamsulosin will be dispensed.
- The subject will complete the following questionnaires:
- The AUA symptom score
- BPH Impact Scale
- Bladder Function
- Erectile Function
- Ejaculatory Function
- Dispense an antibiotic

7 Visit 7: End of Study (3 months post-injections \pm 3 days)

- A physical including a digital rectal exam (DRE) will be performed.
- The subject's concomitant medications will be discussed and documented.
- Any adverse events experienced by the subject will be documented.

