Mean AUA score reduction in the alpha blocker group is expected to be at most 9.6 with a standard deviation of 6.3 based on published results of a randomized trial comparing tamsulosin versus placebo.²⁹ However, that same study showed a strong pill placebo effect with a mean reduction of 5.5, resulting in a treated reduction of 4.1 above the placebo group. Another study¹³, comparing botulinum toxin to placebo, showed a mean score reduction in the botulinum group of 15.2 and no placebo change. For our study, we will assume a mean reduction of 15.2 in the onaBoNT-A group which is 9.7 more than the pill placebo effect, a mean reduction of 9.6 in the alpha blocker group and a standard deviation of 6.3 for both groups. Based on these assumptions, a sample size of 29 subjects per group will achieve 90% power to detect a difference of 5.6 with an alpha level of 0.05 using the 2-sided independent t-test. Sample size calculations were done using PASS 2008 software (Hintze, J. (2008). NCSS, LLC. Kaysville, Utah. www.ncss.com).

The drop-out rate in the alpha-blocker study was as large as 20% and our own experience with onabotulinumtoxinA (onaBoNT-A) in the MIST-2 trial has demonstrated a dropout rate of 14%. So adjusting our sample size for an expected dropout rate of 20%, we will enroll 37 patients into the onaBoNT-A and tamsulosin groups for a total of 74 patients. To address some of the problems with possible attrition bias, we will use intent to treat analysis and patients will be kept in the study as long as possible even if they are no longer on treatment. We will also compare results between the intent to treat groups and the subjects who completed treatment to determine if differences exist.

XII. RETENTION AND DROPOUT/WITHDRAWAL

Minimal dropout or loss to follow-up is expected in this cohort, especially given the short follow-up. However, if a patient drops out before 4 weeks, he will be replaced so that the required sample size is realized. For purposes of tracking the feasibility of conducting a trial of treatment with onaBoNT-A, reasons for dropout or withdrawal will be documented.

XIII. CRITERIA FOR DISCONTINUING THE STUDY

- A Subjects unable to tolerate [tamsulosin or] onaBoNT-A due to side effects.
- B Subjects can request removal from the study for any reason at any time.
- C Subjects may be withdrawn at any time at the discretion of the investigator for safety, compliance, or other reasons.

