A discontinuation occurs when an enrolled subject ceases participation in the study, regardless of the circumstances, prior to completing the protocol.

The reasons for a subject discontinuing from the study will be recorded in the Case Report Form.

XIV. DATA ANALYSIS

Analysis will begin with descriptive statistics. Implausible and missing values will be identified and double-checked for accuracy. Parametric methodology will be used unless measurements have tested positive for violation of normality assumption. The differences between the study subjects groups will be evaluated using the paired-samples t-tests. The clinical outcomes will be compared using Fisher's test. The criterion for significance (alpha) has been set at 0.05. All tests are 2-tailed, which means that an effect in either direction will be interpreted. Analysis will be conducted using SPSS 17.0. ("SPSS Statistics 17.0", SPSS Inc., Chicago, IL, 2008).

XV. RISKS AND DISCOMFORTS

- A BOTOX®: It is expected that some participants may have some or all of the following side effects when given BOTOX®. Other side effects may occur which were not seen before. Side effects are usually temporary and manageable. However, it is possible they could cause serious disease or death. The study may include risks that are unknown at this time.

There have been rare reports of serious and/or immediate or even deadly abnormally sensitive reactions after treatment with BOTOX. These reactions include allergic reaction, skin rash, itching, swelling, and difficulty in breathing.

It is a rare possibility that the injection of BOTOX® could lead to botulism. The classic symptoms of botulism include double vision, blurred vision, drooping eyelids, slurred speech, difficulty swallowing, dry mouth, and muscle weakness. The doctor's examination may reveal that the gag reflex and the deep tendon reflexes like the knee jerk are decreased or absent.

There have been rare reports of sudden death, sometimes associated with difficulty in swallowing or pneumonia. There have also been rare reports of heart problems (including irregular heart beats and heart attack, some resulting in death). Some of these patients were already at risk for heart disease. It is not known if BOTOX actually caused these problems.

It should not be used when infection is present at the injection site or in people known to be abnormally sensitive to BOTOX.

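### The intent-to-treat commitment is left unprotected: the 4-week replacement rule has no starting point, the discontinuation text can be read to end follow-up, and no method is given for a missing 3-month AUASS

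*Combined protocol and SAP*

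**What the plan says.** **Commitment (XI. Sample Size).** The analysis is to be intent-to-treat, and "patients will be kept in the study as long as possible even if they are no longer on treatment". XI also promises to compare the intent-to-treat result with that in men who completed treatment. The sample size is 29 per group, then inflated: "So adjusting our sample size for an expected dropout rate of 20" per cent, giving 37 per group and 74 in total. XI cites dropout of up to 20% in the alpha-blocker study and 14% in the site's earlier onaBoNT-A trial.

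**Replacement (XII. Retention and Dropout/Withdrawal).** "if a patient drops out before 4 weeks, he will be replaced so that the required sample size is realized". The same section expects little dropout because follow-up is short.

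**Discontinuation (XIII. Criteria for Discontinuing the Study).** The first criterion is "Subjects unable to tolerate [tamsulosin or] onaBoNT-A due to side effects". The section then adds: "A discontinuation occurs when an enrolled subject ceases participation in the study, regardless of the circumstances, prior to completing the protocol".

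**Timing (VIII. Design, Procedures).** The visit headings include "Visit 3: Injection (4 weeks post-biopsy" and "Visit 6: (4 Weeks post-injection". The urine check at Visit 3 is done "prior to randomization and preparing onaBoNT-A solution to ensure that no infection is noted or suspected", which places randomisation at Visit 3.

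**Analysis (X. Statistical Analysis; XIV. Data Analysis).** The primary analysis is a two-sided independent t-test on change in AUASS from baseline to 3 months. On missing values, XIV says only that they will be identified and checked for accuracy.

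**The concern.** Intent-to-treat needs three things: every randomised man stays in his assigned arm, outcome collection continues after treatment stops, and there is a stated way to handle scores that are still missing. XI states the principle. XII, XIII and X each leave one of these open.

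At stake is which men stand behind the primary result. If early leavers could be substituted, intolerant men lost to follow-up, and the rest analysed only where a 3-month score exists, the comparison would move towards men who stayed. If leaving is related to arm or to outcome, the estimated difference can be biased. The choice of method could also be made after the data are seen.

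**Working it through.** **1. Where the 4 weeks could start.** The schedule has two 4-week intervals, one on each side of randomisation.

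| Start | End | Relation to randomisation | Effect of replacement |
|---|---|---|---|
| Biopsy (Visit 2) | Injection (Visit 3) | Before | None on intent-to-treat |
| Injection (Visit 3) | Visit 6 | After | Breaches intent-to-treat if the original man leaves the analysis set |

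XII does not choose between them. It does not say whether a replaced man stays in the analysis.

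**2. XI beside XIII.** XI keeps men in the study after treatment stops. XIII lists intolerance of treatment as a criterion for discontinuing the study, and defines discontinuation as ceasing participation. Nothing separates stopping treatment from leaving the study. Read strictly, XIII ends follow-up that XI continues. Read permissively, the two coexist.

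**3. Missing 3-month scores.** X names the test, XIV names a data check, and XI adds the completer comparison. None assigns a value or a model to a missing score. The t-test as written would most naturally use men with an observed score. That is an inference.

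**4. The plan's own figures.** Inputs from XI: mean reductions 15.2 and 9.6 (difference 5.6), SD 6.3, two-sided alpha 0.05, power 90%.
- Standardised difference: 5.6 / 6.3 = 0.889.
- The two-sample t-test needs 27.6, so 28 per arm. At 29 per arm power is 91.4%. The stated 29 is reproduced to within one man.
- Inflation: 29 / 0.8 = 36.25, so 37 per arm.

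**5. Is replacement of randomised men needed for power?** Take 37 per arm, no replacement, and assume that 5.6 and 6.3 hold among men with an observed score. Average the t-test power over the binomial number observed.
- 20% loss: 37 × 0.80 = 29.6 expected per arm, average power 91.7%.
- 14% loss: 37 × 0.86 = 31.8 expected per arm, average power 93.6%.
- At 20% loss both arms reach 29 observed in only 47% of trials, yet average power stays above 90%.

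**6. How much could the handling of missing scores matter?** Assume 37 per arm, all randomised men analysed, and every missing 3-month change drawn with mean L = 0 (no change) or L = 5.5 (the pill-placebo reduction quoted in XI), SD 0 or 6.3. With loss p1 on onaBoNT-A and p2 on tamsulosin:

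Difference = [(1 − p1) × 15.2 + p1 × L] − [(1 − p2) × 9.6 + p2 × L]

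Example, 20% in both arms, L = 0: 0.8 × 15.2 − 0.8 × 9.6 = 12.16 − 7.68 = 4.48. With equal loss L cancels, so L = 5.5 also gives 4.48.

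Example, 20% onaBoNT-A and 14% tamsulosin, L = 0: 12.16 − 0.86 × 9.6 = 12.16 − 8.256 = 3.90. With L = 5.5, add (0.20 − 0.14) × 5.5 = 0.33, giving 4.23.

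Power by simulation (100,000 trials per scenario):

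| Loss onaBoNT-A / tamsulosin | Difference | Power, range over L and SD |
|---|---|---|
| 14% / 14% | 4.82 | 75-89% |
| 20% / 20% | 4.48 | 65-85% |
| 14% / 20% | 5.06-5.39 | 83-93% |
| 20% / 14% | 3.90-4.23 | 55-80% |

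The documents do not give the loss split by arm or the leavers' change. Both are assumed.

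**The case against.** The strongest reply is that XI already governs. It sets intent-to-treat, promises off-treatment follow-up and adds a completer comparison. XII is about enrolment and says nothing of removing anyone. XIII is a bare list with a definition that serves the case report form. Read together, a replaced man stays in the analysis and an intolerant man can still be followed. OnaBoNT-A is also a single injection, so after Visit 3 a man in that arm has only placebo capsules left to stop.

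Much of this stands. A reader might infer that XII removes randomised men or that XI and XIII flatly contradict each other. Each holds on one reading only, and the documents do not settle which applies. The completer comparison is a real, if partial, safeguard.

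A reader might also call replacement on top of the 20% inflation an error in itself. It is not: enrolling more men than needed harms neither validity nor power, and replacement would raise the chance of reaching 29 per arm. The problem is confined to displacing a randomised man.

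It can also be said that a missing-score rule for the t-test would close the gap without a new model. It would close the gap in wording. The model's advantage is that it uses the 4-week AUASS of men who leave after Visit 6, which a t-test on observed 3-month scores discards.

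What the reply does not answer is the missing score. Intent-to-treat as a label does not supply one, and XI itself plans for 20% dropout.

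**Conclusion.** The point holds: XI's commitment is sound, but XII, XIII and X do not secure it. The set of men behind the primary result and the treatment of missing 3-month scores are not fixed in advance.

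The sample size is not at fault. It reproduces, and without replacement average observed-score power is about 92% at 20% loss and 94% at 14%. This assumes that the planned difference and SD hold among the men observed.

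If all missing scores are set to 0 or 5.5, the difference falls to 4.48 with power of 65-85% at 20% loss in both arms. It falls to 3.90-4.23 with 55-80% if loss is 20% on onaBoNT-A and 14% on tamsulosin. A reader might take these figures to mean that the trial is underpowered, or treat them as limits. They are neither. They are assumed scenarios for the sensitivity analyses, not bounds and not the power of the proposed primary model. Nor can one say which arm would be favoured: the direction and size of any bias cannot be derived from the documents.

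One figure should not be used as a dropout rate. In Preliminary Studies, 125 of 134 men gave complete primary outcome data. That describes completeness of an outcome combining AUASS and Qmax, not stated dropout.

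This should be fixed before analysis, but it does not call the design into question.

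**What to change.** - **XII.** Limit replacement to men lost before randomisation at Visit 3, or state that any replaced randomised man stays in the analysis set in his assigned arm.
- **XI and XIII.** Reconcile them so that stopping study treatment does not by itself end AUASS collection at the scheduled 4-week and 3-month visits. This changes nothing about who stops treatment.
- **X, primary analysis.** Define the primary set as all randomised men as assigned. Estimate the 3-month difference with a repeated-measures model on the scheduled baseline (screening), 4-week and 3-month AUASS. Keep the t-test on observed scores and the completer comparison as supportive.
- **X, sensitivity.** The model gains no post-treatment information on men lost before Visit 6. Pre-specify two analyses in which all men with a missing 3-month score are given no change, or a change of 5.5.
- **XI, power.** State that the 90% refers to 29 men per arm with observed 3-month scores.

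**Cost.** Protocol wording, one standard model on data already scheduled, and two extra runs, with no added patients or visits. The downsides are that the model assumes data are missing at random, the sensitivity analyses can fall below 90% power, and the power statement becomes narrower.

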- C Urine specimens collected for dipstick analysis during the screening visit are routine for patients with BPH and LUTS and will be handled according to standard of practice. The test results will be included in the subject's research and medical charts.

X. STATISTICAL ANALYSIS

The primary endpoint, change in AUASS score from baseline to 3 months, between the onaBoNT-A and tamsulosin groups will be analyzed using the 2-sided independent t-test.

Baseline measures of the data such as age and ethnicity as well as secondary endpoints will be examined using summary statistics to determine if any differences exist between the 2 study groups.

Graphical methods will be used to access distributional properties of the secondary endpoints (urinary flow rate, serum PSA, prostate volume symptom relief, post-void residual, BPH impact score, Bladder Function, Erectile Function and Ejaculatory Function questionnaires). If extreme departures from normality are found, use of non-parametric analytical methods such as the Wilcoxon rank-sum test or transformation of the data will be considered. Questionnaire scores will be examined for reliability using Cronbach's alpha. The distributions of the scores will be examined to see if they are evenly distributed around the mid-point of the scales or are clustered at the top or bottom of the scales (ceiling or floor effect). If strong ceiling or floor effects are found, this could limit the usefulness of these measures. Changes in these secondary endpoints will be assessed using either the independent t-test or its non-parametric equivalent, the Wilcoxon rank sum-test. Statistical analysis will be done using SAS, version 9.2 (SAS Institute, Cary NC).

The endpoints apoptotic index, proliferation index, nerve density, stromal reactive indexes, and vessel density, will be checked for their distributional properties using the methods described for the data collected in Aim 1. Change from baseline to 3 months will be analyzed using either the 2 sided t-test or the Wilcoxon rank sum test.

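### Section XIV makes parametric testing depend on an unspecified normality test and does not exempt the primary endpoint, to which Sections X and XI give an unconditional t-test

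*Combined protocol and SAP*

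**What the plan says.** Three sections of the combined protocol and SAP bear on the primary test.

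- **Section X (Statistical Analysis)** defines the endpoint, "The primary endpoint, change in AUASS score from baseline to 3 months", and says that the comparison of the two arms "will be analyzed using the 2-sided independent t-test". No condition is attached. Distribution checks come in a separate paragraph with a narrower scope: "Graphical methods will be used to access distributional properties of the secondary endpoints". The trigger there is a strong one, and the alternatives, which include transformation, are only to be considered: "If extreme departures from normality are found, use of non-parametric analytical methods such as the Wilcoxon rank-sum test". A later paragraph extends the same checks to the tissue endpoints.
- **Section XI (Sample Size)** plans 29 per group for 90% power to "detect a difference of 5.6 with an alpha level of 0.05 using the 2-sided independent t-test".
- **Section XIV (Data Analysis)** sets a rule for measurements in general: "Parametric methodology will be used unless measurements have tested positive for violation of normality assumption". The next sentence reads "The differences between the study subjects groups will be evaluated using the paired-samples t-tests". Section XIV also names SPSS 17.0, where Section X names SAS 9.2.

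**The concern.** Section X applies its distribution checks to the secondary and tissue endpoints only, by graph, and acts only on extreme departures. Section XIV applies to measurements without limit and acts on a positive test result. The two rules differ in scope, in trigger and in consequence, and no sentence ranks one section above the other.

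Section XIV also leaves out what would make its rule reproducible: which normality test, at what level, applied to each arm, to pooled data or to residuals, and what replaces the parametric method. Each would have to be chosen with the data in hand. Two analysts could each follow the document and run different primary tests, one giving a mean difference in AUASS points and the other perhaps a rank comparison. What is at stake is whether the primary test and its effect measure are fixed in advance.

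**Working it through.** **1. The plan's own figure.** Inputs from Section XI: difference 15.2 − 9.6 = 5.6, SD 6.3, two-sided alpha 0.05, power 90%, dropout 20%.

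- Normal approximation: n = 2(1.960 + 1.282)² × (6.3/5.6)² = 26.6, so 27 per group.
- Exact noncentral t with n = 29: noncentrality = (5.6/6.3) × √(29/2) = 3.385 on 56 df, power 91.4%. With n = 28, power is 90.4%.
- Dropout: 29/(1 − 0.20) = 36.25, so 37 per group and 74 in total.

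The stated size is reproduced to within one patient per group, and it rests on the independent t-test.

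**2. What the Section XIV rule would do.** Section XIV specifies no procedure, so one has to be assumed: Shapiro-Wilk at 0.05 in each arm; if either arm rejects, the Wilcoxon rank-sum test, otherwise the independent t-test. Simulation with 29 per arm, SD scaled to 6.3, a location shift between arms, and 3,000 trials per setting (simulation error near 5% is about ±0.8 points):

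| Outcome shape | Switch rate | Two-stage type I error | Tests disagree at 5.6 points | Power at 5.6: t-test / two-stage |
|---|---|---|---|---|
| Normal | 10–11% | 4.4% | 4.0% | 91.5% / 91.4% |
| Normal, rounded to integers | 11–12% | 4.9% | 3.5% | 91.6% / 91.4% |
| Moderate skew (gamma, shape 4) | 67–69% | 5.3% | 4.4% | 91.1% / 93.2% |
| Heavy tails (t, 5 df) | 43–44% | 4.4% | 5.2% | 91.0% / 94.0% |
| Exponential | over 99% | 4.7% | 7.4% | 91.5% / 98.9% |

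**3. Repeat check.** A second run used 6,000 trials per setting.

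- Rounded normal: switch rate 10–12%, disagreement at 5.6 points 3.0%.
- A bounded integer score (assumed scale 0–35, baseline mean 21 and SD 5, follow-up clipped to the scale): switch rate 13–15%, two-stage type I error 5.4%, disagreement at 5.6 points 3.8%.
- Gamma, shape 4: switch rate 68%, two-stage type I error 5.5%, disagreement at 5.6 points 4.2%.
- Strong skew, lognormal(0, 0.8), at a 3.5-point shift: power 61% for the t-test and 92% for the two-stage rule.

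**4. Smaller true differences.** At 3.5 points the tests disagree more often: about 7% for normal or near-normal data and about 10% for moderate skew in these runs.

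**The case against.** The strongest reply is that the specific governs the general. Section X names the primary endpoint and its test, Section XI repeats that test, and Section XIV names no endpoint. On that reading there is only a loose sentence. This has force: the rule reaches the primary endpoint by inference from an unrestricted word, not by express statement. It does not settle the matter. Section XIV is a current analysis section with its own alpha, software and between-group test, and nothing makes it defer to Section X.

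Several stronger readings are tempting and are not supported:

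- *That the rule inflates type I error.* Applied mechanically, it stays between 4.4% and 5.5% in every setting above.
- *That the sponsor could report the smaller p-value.* That would give about 5.0 to 6.7%, but no passage permits it. Nor does any passage say when normality would be tested relative to unblinding.
- *That Section XIV switches to a rank test.* It names no replacement. The rank-sum test appears in Section X, for secondary and tissue endpoints, with transformation also offered for the secondary ones.
- *That switching gains nothing.* Under normality it costs almost nothing, and under strong skew it gains appreciable power.
- *That a rank analysis cannot give an effect in score points.* A Hodges-Lehmann estimate would, and under a pure location shift it targets the same quantity. The plan does not name one.

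The reply is also right that the paired-samples sentence is the more serious conflict in the same paragraph. That is a reason to correct both together.

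**Conclusion.** The inconsistency is real and concerns the primary analysis. Sections X and XI commit to an unconditional independent t-test. Section XIV makes parametric methods conditional on an unspecified test of the trial's own data, exempts nothing, and is not subordinated to Section X. The primary test and its effect measure are therefore open until the data are seen.

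The size is modest. The switch rates (about 10 to 15% for near-normal integer scores, about two-thirds for moderate skew) and the 3 to 4% disagreement at 5.6 points depend on the assumed Shapiro-Wilk test at 0.05 in each arm and the assumed rank-sum fallback; another choice would give other rates. Neither type I error nor sample size is materially affected. This is a gap in pre-specification that should be closed, not a threat to the validity of the design.

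**What to change.** In Section XIV:

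1. State that the change in AUASS is compared between arms by the 2-sided independent t-test of Section X whatever any normality test shows, reported as a mean difference in AUASS points with a 95% confidence interval.
2. Name the Wilcoxon rank-sum test as a sensitivity analysis for that endpoint.
3. Limit the normality rule to the secondary and tissue endpoints, using Section X's own criteria. The documents hold no distributional data that would justify prescribing a different method for each secondary endpoint.
4. Delete the paired-samples t-test sentence for differences between groups. The arms are independently randomised, and if the sentence stays, Section XIV still contradicts Section X on the primary comparison.

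The cost is wording only. Planned size stays at 29 evaluable and 37 enrolled per group, with 91.4% power under the stated assumptions. The downside is some loss of power if the change scores prove strongly skewed; the named sensitivity analysis would show whether that matters.
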